### 7.1.2.12 PROMIS SF SD 8b Sleep Questionnaire

The PROMIS SD SF 8b is a short form questionnaire to assess sleep disturbance. It comprises eight questions and will be completed by subjects at Visits 2, 4, 5 and 7. Total score is calculated as sum of individual items. Total score is not calculated if any individual item is missing.

Mean change from baseline to week 4 for each question and the total score will be analysed with an ANCOVA model similar to that used for the primary endpoint.

# 7.1.2.13 Hospital Anxiety and Depression Scale Questionnaire

The HADS tool is used for assessing anxiety and depression which comprises of 14 questions, seven each for anxiety and depression. Total anxiety score is calculated as sum of the seven odd-numbered questions, total depression score as sum of even-numbered questions. Total scores are not calculated if more than one item from that domain is missing. If a single item is missing, then the patient's average score for items available for a specific score is used as the value for the missing item. HADS will be completed by subjects at Visits 2, 4, 5 and 7.

Mean change from baseline to week 4 for the sum of the anxiety and depression questions will, separately, be analysed with an ANCOVA model similar to that used for the primary endpoint separately by cohort.

### 7.1.2.14 Hull Airway Reflux Questionnaire

The Hull Airway Reflux Questionnaire is a 14-item questionnaire that assesses airway hypersensitivity, particularly that associated with reflux of gastric contents. Total score is calculated as sum of individual items. The questionnaire will be completed by subjects at Visits 2, 4 and 7.

Mean change from baseline to week 4 for the total score will be analysed with an ANCOVA model similar to that used for the primary endpoint separately by cohort except only baseline for Period A will be used as there is no baseline available for Period B.

### 7.1.3 Sub-Groups

The primary efficacy endpoint will also be summarised descriptively by the following subgroups, provided there are a minimum of 10 evaluable subjects in each sub-group within the category and cohort:

 Total score increase of ≥5.0 ( et al. Sinha A, Patel AS, Siegert RJ, et alThe King's Brief Interstitial Lung Disease (KBILD) questionnaire: an updated minimal clinically important difference BMJ Open Respiratory Research 2019;6:e000363. doi: 10.1136/bmjresp-2018-000363)

Page 33 of 50

Category	Sub-group
Use of concomitant disease modifying therapies	Yes (using)
(nintedanib or pirfenidone) at baseline	No (not using)
IPF Cough Severity Scale score at baseline	≤ Median
	> Median
Sex	Male
	Female
Race	White
	Non-white
Ethnicity	Hispanic
	Non-hispanic

The awake cough frequency endpoint will also be summarised descriptively in the following sub-group:

By awake cough frequency at baseline (<=Median, >Median)

### 8 SAFETY ANALYSES

Safety data will be summarised descriptively for each treatment. That is, safety data will be summarised for two doses of orvepitant (10 mg and 30 mg separately), and two placebo groups separately by cohort.

No formal inferential tests will be performed on safety data.

Safety analysis will be carried out using the SS population.

### 8.1 ADVERSE EVENTS

Adverse events will be coded using the latest available version of MedDRA (v26.0 or higher). All treatment-emergent AEs (TEAEs) from the start of study drug dosing will be collected. A TEAE is any AE that first occurred or worsened in severity following first dose. AEs that start during the wash-out period will be assigned to the treatment received during Treatment Period A for TEAE reporting; AEs that start following first dose in Treatment Period B up to end of follow-up will be assigned to the treatment received during Treatment Period B for TEAE reporting.

The following AE summaries will be presented:

- An overall summary table, including the number of events and number and percentage of subjects with:
  - o TEAEs
  - Subjects with at least one TEAE
  - Study drug-related TEAEs

Page 34 of 50

- Serious TEAEs
- o TEAEs with an outcome of death
- o Treatment-emergent AESIs
- Severe TEAEs
- o TEAEs leading to study drug discontinuation
- TEAEs by SOC and PT. This table will have a section for overall, and two subgroup sections for concomitant use of disease modifying therapies (yes, no [nintedanib or pirfenidone])
- Serious TEAEs by SOC and PT
- Treatment-emergent AESIs by SOC and PT
- TEAEs leading to study drug discontinuation by SOC and PT
- Related TEAEs by SOC and PT
- Maximum severity of TEAEs by SOC and PT

Non-treatment emergent AEs and TEAEs will be listed.

In addition, the following subject listings will be provided as tables:

- Deaths
- Serious TEAEs
- AESIs
- TEAEs leading to study drug discontinuation

For all AE tables summarised by SOC and PT, a subject contributes only once to the count for a given AE on the SOC level and on the PT level within SOC. SOC and PT levels will be sorted in descending order of frequency (subject count), followed by descending order of frequency (event count), followed by alphabetical order.

AEs will be classified as either related or unrelated to study medication. AEs with missing relationship to study drug are counted as related in the summary tables.

In the summary by severity, subjects reporting AEs at different severities will be counted only once at the highest severity reported within an AE level (SOC or PT). Severity categories will comprise of mild, moderate and severe.

Partial start dates in AEs will be imputed with a conservative algorithm, to the first day of the month (if missing day) or the first month of the year (if missing month). Partial end dates in adverse events will be imputed to the last day of the month (if missing day) or the last month of the year (if missing month). All AEs will be assigned as a TEAE or not based on the imputed dates as appropriate. If the onset date is missing a conservative approach will be applied such that the AE is considered treatment emergent.

Page 35 of 50

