10.5.2 Assessment of Severity

The severity (intensity) of each adverse event will be classified as:

Mild Awareness of sign or symptom, but easily tolerated by the subject

Moderate Sign or symptom causes discomfort, but does not interfere with the subject's

normal activities

Severe Sign or symptom of sufficient intensity to interfere with subject's normal

activities

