11.9 Statistical Methods for Safety Parameters

Safety data will be summarised descriptively for each treatment. No formal inferential tests will be performed on safety data.

The number of treatment emergent AEs (TEAEs), and subjects with TEAEs, will be compared between treatments. TEAEs are defined as AEs that first occurred or worsened in severity after the first dose of IMP.

TEAEs will be summarised for all causality AEs and for treatment-related AEs (those with related relationship to IMP and missing). TEAEs will be summarised by MeDRA body system and preferred term. TEAEs will also be reported by severity.

Any deaths, SAEs and AEs leading to discontinuation of IMP administration will also be summarised by treatment group.

SAEs will be presented in a similar way to AEs.

Vital signs will be summarised for each treatment group by visit. Summary statistics will be presented for absolute values and the change from Baseline.

ECGs will be assessed by the Investigator for abnormal findings. These will be categorised and summarised as normal, abnormal-not clinically significant, or abnormal-clinically significant. ECG intervals will be recorded and summarised as absolute values and changes from Baseline.

Clinical laboratory data for individual subjects will be listed and any out of range values will be highlighted. Laboratory data will be summarised for each treatment group by visit. Summary statistics will be presented for absolute values and change from Baseline, as well as an analysis of shifts from Baseline.

Extent of exposure and compliance will be summarised.

Selected safety parameters will be summarised for the following sub-groups:

- By use of concomitant disease modifying therapies at Baseline (yes, no [nintedanib or pirfenidone])

Protocol No.: ORV-PF-01 Final V4.0 (US) Page 58 of 85

CONFIDENTIAL Protocol No.: ORV-PF-01
NeRRe Therapeutics Ltd

Product: ORVEPITANT

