### **5.2.2** Baseline Values

Baseline values will be defined separately for each treatment period, unless stated otherwise.

For the primary efficacy endpoint (mean change from baseline to Week 4 in weekly average of the daily IPF Coughing Severity Scale score), period-specific baseline will be used in the analysis, which is the average of the 7 calendar days up to and including the date of Visit 2 for Treatment Period A and the average of 7 calendar days up to and including the date Visit 5 for Treatment Period B.

For secondary efficacy endpoints related to change from baseline, the period-specific baseline will be used when available; for those endpoints for which a period-specific baseline is not available

(cough frequency and Hull Airway Reflux Questionnaire), the baseline in Treatment Period A will be used.

For safety assessments, baseline will be Visit 2 for Treatment Period A and for Treatment Period B it will be Visit 5.

For both safety and efficacy assessments, if the period-specific baseline is missing for Treatment Period A the value from Visit 1 will be used. If this is missing change from baseline will not be calculated. If the period-specific baseline is missing for Treatment Period B the value from Visit 2 (first preference) or visit 1 (second preference) will be used. If both are missing change from baseline will not be calculated.

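### SAP 8.1 counts a worsening as treatment-emergent but allocates adverse events by start alone, so a Period B worsening of an earlier event reaches the Period B treatment only if entered as a new record

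*SAP*

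**What the plan says.** SAP 8.1 defines the term: "A TEAE is any AE that first occurred or worsened in severity following first dose". Protocol 11.9 has the same two limbs: "TEAEs are defined as AEs that first occurred or worsened in severity after the first dose of IMP". In both, the clock is one first dose for the whole study, although each subject who enters both periods has a first dose in each.

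The next sentence of SAP 8.1 allocates events to treatment, and it speaks only of starts. For the wash-out: "AEs that start during the wash-out period will be assigned to the treatment received during Treatment Period A for TEAE reporting". For the second period: "AEs that start following first dose in Treatment Period B up to end of follow-up will be assigned to the treatment received" in Period B. The treatment for an event that starts during Period A dosing is implied rather than stated.

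In the severity table a subject is "counted only once at the highest severity reported within an AE level (SOC or PT"). Status as a TEAE is set from dates: "All AEs will be assigned as a TEAE or not based on the imputed dates as appropriate". The dates concerned are start and end dates; no date of worsening is mentioned.

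On data collection, Protocol 10.5.2 says "The severity (intensity) of each adverse event will be classified as" mild, moderate or severe. Neither that section nor Protocol 10.5.4 says what a site does when an ongoing event changes grade.

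Other safety data are handled by period. SAP 5.2.2 has: "For safety assessments, baseline will be Visit 2 for Treatment Period A and for Treatment Period B" it is Visit 5.

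**The concern.** The definition and the allocation rule do not match. A single first dose with an onset-or-worsening definition suits a parallel-group trial, where any later worsening can belong to only one treatment. In a crossover, an event can begin on one treatment and worsen on the other, and a rule keyed to the start does not follow it.

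Safety is a primary objective, and Protocol 8.6.1 says that safety findings will be compared with a placebo period. The by-treatment adverse event tables are that comparison. Laboratory values, vital signs, ECG and lung function are each given a new baseline at Visit 5; adverse events are not. The protocol describes IPF as progressive, so some events may still be present after a three-week wash-out and then worsen. The severity table is the most exposed, but the serious, AESI and discontinuation tables take their treatment from the same allocation sentence.

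**Working it through.** The documents state no figure on this point, so there is none to reproduce. The check applies the written rule to each type of event.

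**Step 1. The rule read literally.**

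| Event | TEAE under SAP 8.1? | Treatment under SAP 8.1 |
|---|---|---|
| Starts during Period A dosing, no later change | Yes, by onset | Period A (implied) |
| Starts in wash-out, no later change | Yes, by onset | Period A (stated) |
| Starts after first Period B dose | Yes, by onset | Period B (stated) |
| Starts in Period A or wash-out, worsens in Period B | Already yes, by onset | Period A by its start; no rule for the worsening |
| Starts before any dose, worsens after dosing | Yes, by worsening | None stated |

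With one study-wide clock, the worsening limb changes the status of the last row only, and that row has no allocation. Such events can occur, because Protocol 10.5.4 records adverse events from Screening.

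**Step 2. The effect of the recording convention.** Take an event that is mild in Period A and becomes severe in Period B.

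| How the worsening is recorded | Under Period A treatment | Under Period B treatment |
|---|---|---|
| (i) One record, maximum severity kept | Severe | Nothing |
| (ii) One record, onset severity kept | Mild | Nothing |
| (iii) New record with its own start date | Mild | Severe |

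Convention (i) places the worst grade under the Period A treatment. Convention (ii) loses the worsening altogether. Convention (iii) is correct.

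**Step 3. Effect on the contrast.** Within a cohort, let *a* be the number of subjects on the placebo-first sequence whose event starts on placebo and becomes severe on orvepitant. Let *b* be the number on the orvepitant-first sequence whose event starts on orvepitant and becomes severe on placebo. Assume none of them has another severe event at the same table level. Their contribution to the severe count, orvepitant minus placebo, is:

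- true value: *a* − *b*
- under (i): *b* − *a*, the same size with the sign reversed
- under (ii): 0
- under (iii): *a* − *b*

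The documents give neither *a* nor *b*, so the distortion has a known form but no known size.

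**Step 4. Could residual Period A drug justify the rule?** Inputs: half-life about 33 hours (Protocol 8.6.1, SAP 2.6.4) and wash-out 21 ± 3 days (Protocol 8.7.5). Half-lives elapsed = days × 24 / 33; fraction left = 0.5 raised to that number.

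- 18 days: 432 / 33 = 13.1 half-lives, about 0.011% left
- 21 days: 504 / 33 = 15.3 half-lives, about 0.0025% left
- 24 days: 576 / 33 = 17.5 half-lives, about 0.0006% left

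On the plan's own pharmacokinetics, remaining Period A drug is not a reason to keep a Period B worsening with the Period A treatment.

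**The case against.** The best reply is that this is silence, not an instruction to misassign. The allocation sentence is not a complete algorithm, since it leaves even events starting during Period A dosing to be inferred. Sites may enter each worsening as a separate event. The severity rule expects subjects with events at different grades, which fits several records, and Protocol 10.2.2 has worsening examination findings recorded as adverse events. Completion instructions for the eCRF are not among the documents, and SAP 13.1 places dataset specifications after the SAP. The AESI examples of respiratory decline are separate healthcare visits, which would naturally carry their own onset dates. Safety is descriptive, and SAP 8.1 lists all events, with subject listings for deaths, serious TEAEs, AESIs and discontinuations.

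Much of this stands. A reader might infer that every event worsening in Period B is reported, at its worst grade, under the wrong treatment. The documents do not support that: it follows only under convention (i), which they neither state nor exclude. The descriptive setting also means that no test or error rate is affected.

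The reply does not close the gap. Protocol 10.2.2 concerns examination findings only, and Table 2 schedules examinations at Screening, Baseline and Follow-up, not at the treatment-period visits. The severity rule is compatible with separate records but does not require them. Listings let a reader trace a single case; they do not correct the tables. The pre-dose event that worsens lacks a treatment when it is held in one record, whichever grade that record keeps.

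**Conclusion.** The concern holds as a mismatch between definition and allocation. SAP 8.1 admits worsening into the TEAE definition but gives it no route to a treatment. An event that starts in Period A and worsens in Period B is not allocated to the Period B treatment, and a pre-dose event that worsens after dosing has no stated treatment. Whether the tables come out wrong depends on how sites record a worsening, which the documents leave open for adverse events in general. Two of the three conventions give a wrong table and one does not.

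The size is unknown. It is tempting to illustrate it with a number of misplaced severe events per cohort, but no adverse event rates are given and any such count would be invented. Nor should the argument rest on safety comparison being the reason for the crossover: Protocol 8.6.1 gives that reason as assessing efficacy with fewer subjects, and mentions the safety comparison separately.

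This is more than a missing detail, because the by-treatment tables report a primary objective, the possible bias can reverse the contribution of these events, and the plan already resets baseline by period for its other safety data.

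**What to change.** In SAP 8.1:

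- Define treatment-emergence per period. An event is treatment-emergent for a period if it starts, or rises above its grade before that period's first dose, between that first dose and the first dose of the next period (or the end of follow-up).
- Allocate the worsening and its grade to that period's treatment, and keep the earlier grade with the earlier treatment. A pre-dose event that worsens goes to the period in which it worsens.
- State that a worsening is identified by its own dated record.

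The text is a few sentences. SAP section 1 already allows for revision after protocol amendments, and the SAP is based on protocol Versions 3.0/3.1 while the protocol supplied is V4.0.

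There are two costs. One persistent event can count once under each treatment, which a table footnote should say. Also, the trial is under way (the sample size re-estimation has been done on 25 subjects), so a new instruction to sites cannot supply dates that were never captured. For those events the allocation must be made from the listings at the blinded data review. This does not require unblinding, because it assigns a worsening to a period and not to a named treatment.

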### 6.4 PRIOR AND CONCOMITANT MEDICATIONS

Prior medications are defined as medications that started and stopped before the date of first dosing with study medication. Any medication that started on the date of dosing will not be considered prior. Any medication that stopped on the date of dosing will be considered prior.

Concomitant medications are defined as all medications (excluding study treatment) started or ongoing on/after the date of first dosing with study drug. Medications started or ongoing on/after the date of first dosing in Period A or during the wash-out period will be considered as concomitant medications for Period A; Medications started or ongoing on/after the date of first dosing in Period B up to end of follow-up will be considered as concomitant medications for Period B. Partial start dates in prior and concomitant medications will be imputed with a conservative algorithm, to the first day of the month (if missing day) or the first month of the year (if missing month). Partial end dates in prior and concomitant medications will be imputed to the last day of the month (if missing day) or the last month of the year (if missing month). If the year is missing from the start date the medication will be considered to have been started before the date of Visit 1 for that subject.

Prior and concomitant medications will be coded by using the latest available Anatomical Therapeutic Chemical (ATC) Level 2 classification code and preferred drug name according to the World Health Organization Drug Dictionary (WHODrug) Global (March 2023 or higher). Prior and concomitant medications will be sorted by subject ID and then by start date.

Separate summary tables will be provided for prior and concomitant medications, presenting the number and percentage of subjects by each dose group; the summaries will be sorted by ATC Level 2 and PT in descending order of frequency in the overall column (in case of a tie, alphabetical order will be followed). For each subject, the medication will be counted only once within a given ATC level 2 and only once within a given preferred drug name level. A subject may appear more than once if he/she has more than 1 concomitant medication coded under different ATC categories; however, the subject will be counted only once in the overall category.

All medications will be listed.

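### SAP 8.1 dates a partial AE start to the 1st of the month with no floor at first dose, so some on-treatment AEs drop out of the TEAE tables

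*SAP*

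**What the plan says.** SAP 8.1 defines the event class: "A TEAE is any AE that first occurred or worsened in severity following first dose". Protocol 11.9 agrees: "TEAEs are defined as AEs that first occurred or worsened in severity after the first dose of IMP".

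For incomplete dates SAP 8.1 says "Partial start dates in AEs will be imputed with a conservative algorithm, to the first day of the month (if missing day", with the first month of the year used when the month is missing. Incomplete end dates go to the last day of the month or the last month of the year. Then: "All AEs will be assigned as a TEAE or not based on the imputed dates as appropriate". For an AE with no start date: "If the onset date is missing a conservative approach will be applied such that the AE is considered treatment emergent".

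Treatment is attributed by start date: "AEs that start during the wash-out period will be assigned to the treatment received during Treatment Period A for TEAE reporting". AEs that start after the first Period B dose, up to the end of follow-up, go to the Period B treatment.

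SAP 5.3.1 only refers back to 8.1 for AE dates, and the protocol has no AE date rule. Neither document sets a lower limit at first dose or gives the imputed end date a role in TEAE status.

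**The concern.** TEAE status depends on when an AE first occurred or worsened. Moving an unknown day back to the 1st is the choice most likely to place the AE before dosing. For the month of first dose it does so almost always. Protocol 10.5.4 collects AEs from Screening, so a pre-dose date is valid data and would not be queried as impossible.

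The rule also contradicts its own aim. An AE known to have started in the dosing month is removed, while an AE about which less is known, because it has no date at all, is retained.

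Safety is one of the two primary objectives, and the TEAE tables are its main summary. An affected AE leaves the overall counts and the tables by SOC and preferred term, relatedness, severity and discontinuation. With about 44 subjects per cohort (88 in two equal cohorts, Protocol 7.1), a few events can change a preferred-term row.

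**Working it through.** The plan gives no figure to reproduce, so the check applies the rule to the study calendar.

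**Example.** First dose on 10 March; AE onset on 20 March, recorded with the day missing. The imputed start is 1 March, 9 days before dosing, so the AE is not a TEAE.

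**Inputs.** Visit 2 is Day 0 and the first Period A dose is Day 1 (SAP 5.2.1). Nominal Visit 4 is Day 28, Visit 5 is Day 49, the first Period B dose is Day 50, Visit 7 is Day 77 and Visit 8 is Day 91; each visit window is ±3 days (Protocol 8.7 and Table 2). Assumptions: first-dose dates spread evenly over 1,461 consecutive days (2022 to 2025), AE onset uniform over days, month and year known, no worsening recorded.

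**Onset days lost per subject.** If the first dose is on day m of a month with L days, every onset from the dose to month end is lost, that is L − m + 1 days for m ≥ 2 and none for m = 1. The mean over a month is (L − 1)/2. Over four years there are 28 months of 31 days, 16 of 30, three of 28 and one of 29:

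- (28 × 31 × 15 + 16 × 30 × 14.5 + 3 × 28 × 13.5 + 29 × 14) / 1,461 = (13,020 + 6,960 + 1,134 + 406) / 1,461 = 14.73 days.

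**Share of day-missing AEs lost.**

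| Onset window | Days | Share lost | Range over 81 allowed schedules |
|---|---|---|---|
| First dose to Visit 8 | 91 | 14.73/91 = 16.2% | 14.3% (14.73/103) to 18.6% (14.73/79) |
| Period A dosing days | 28 | 14.66/28 = 52.4% | 47.5% to 57.3% |
| Period A plus wash-out | 49 | 14.73/49 = 30.1% | 26.8% to 34.3% |
| Period B plus follow-up | 42 | 0 | 0 |

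The numerator 14.66 is smaller because, in a 30- or 31-day month with a very early first dose, a few lost days fall after Day 28. Day-by-day enumeration gives the same results. The 81 schedules take each of Visit 4, wash-out length, Visit 7 and Visit 8 at its lower limit, target and upper limit.

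**Number of AEs.** The documents do not say how many dates will be partial. On an assumed 200 post-dose AEs with the day missing in 2%, 5% or 10%, the loss is 200 × 0.02, 0.05 or 0.10 × 0.162 = 0.6, 1.6 or 3.2 AEs.

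**What a floor would cost, in the same units.** True pre-dose onsets in the first-dose month could become TEAEs. Counting Screening to Day 0, these are 0.507 × 29 = 14.7 days for a 28-day screening period and 0.737 × 15 = 11.1 days for a 14-day one, before excluding AEs that ended before first dose. The floor recovers about 14.7 true post-dose onset days.

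**Period B.** By the same arithmetic, 14.73/42 = 35.1% of day-missing Period B and follow-up onsets (30.7% to 40.9%) are dated before the first Period B dose and go to the Period A treatment.

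**The case against.** Much can be said for leaving this to the programming stage. SAP 8.1 applies imputed dates as appropriate and declares a conservative intent, and SAP 13.1 leaves dataset specifications still to be written and approved. AEs are reviewed at every visit, two to three weeks apart, and SAEs are reported within 24 hours, so undated events should be few. Safety is descriptive, non-treatment-emergent AEs are listed, and the deaths and AESI listings are not limited to TEAEs. The floor is also a choice of error direction: with equal AE rates before and after dosing it could add nearly as many false TEAEs as it recovers true ones.

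The limits on size stand. So does the trade-off, although its upper end relies on AE recording from Screening, as Protocol 10.5.4 has it, and end dates will remove some of the false cases. The wording argument does not stand: the phrase states no rule, and two programmers coding independently (SAP 13.2) cannot derive a floor that is not written.

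Three stronger readings are tempting and are not supported:

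- **Bias towards orvepitant.** Sequences are randomised 1:1, so Period A is placebo for about half the subjects, and the expected share lost is the same on both treatments.
- **The Period B default as an error.** Attribution by start date plus the 1st-of-month rule is crude but determinate. The SAP does not say whether the result is intended; that calls for confirmation only.
- **A medication rule that works harmlessly and was misapplied to AEs.** SAP 6.4 has the same wording ("Partial start dates in prior and concomitant medications will be imputed with a conservative algorithm"), and a medication counts as concomitant if "started or ongoing on/after the date of first dosing with study drug", so an early start does not remove it. But 6.4 also assigns medications to Period A or B, so back-dating can affect that assignment.

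**Conclusion.** The concern holds as under-counting. As written, a day-missing AE in the month of the first Period A dose becomes non-treatment-emergent unless dosing began on the 1st or worsening is recorded. The missing-month rule has the same defect but should rarely be needed in a study of at most 17 weeks.

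Under uniform onset, 16% of day-missing post-dose AEs are lost (14.3% to 18.6%), all of them early: 52% of those on Period A dosing days and none in Period B or follow-up. These shares are conditional on a date being partial. The absolute effect is probably a few AEs, which remain visible in the listings. It should be corrected because a stated rule gives a result opposite to its stated aim on a primary objective, and the correction is cheap.

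One smaller gap is real: a TEAE with no onset date has no treatment assigned, although SAP 8 tabulates safety by treatment and attribution needs a start date.

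**What to change.** Amend SAP 8.1 before unblinding:

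1. If the known part of the start date is compatible with onset on or after the first Period A dose, and the end date (imputed if partial) does not precede that dose, impute the later of (a) the 1st of the month, or 1 January if the month is missing, and (b) the first Period A dose date. Count the AE as a TEAE. SAP 5.3.3 already supplies a first-dose date when the reported one is missing, so the floor can be computed.
2. Name the treatment to which a TEAE with a wholly missing onset date is assigned.
3. Confirm that a day-missing date in the month of the first Period B dose is meant to default to the Period A treatment, or state another rule. The floor in item 1 does not change this default.
4. Footnote the number of AEs affected in the TEAE tables.

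The cost is a few lines of text and a small change to the AE dataset derivation. The price in accuracy is the exposure of about 11 to 14.7 screening onset days per subject to false TEAE status, before end-date exclusions, against about 14.7 true post-dose onset days recovered. That errs in the conservative direction the SAP says it wants.
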